## **6.2 Event Reporting**

The investigator is required to report all SAEs within 72 hours and any UADEs/USADE's within 24 hours after first learning of the event to the Sponsor. The primary method of reporting SAEs will be through the eCRFs. If the database is unavailable the investigator may send the information to the SAE Hotline. As soon as the database becomes available, the investigator must complete data entry. The investigator will send all available supporting documentation (blinded/de-identified as to the subjects' identity) to the Sponsor.

As additional information becomes available, copies of that source documentation which contain significant information related to the event such as progress notes, consultations, nurse's notes, operative reports, imaging studies and subject summaries etc. are requested for a complete evaluation of the event.

In regard to subject deaths, it is requested that a copy of the death certificate and a copy of the autopsy report, if applicable, be sent to the Sponsor when available. Any other source documents related to the death should also be provided to the Sponsor. In the event that no source documents are available, the PI is requested to describe the circumstances of the subject's death in a letter, e-mail or other written communication.

UADEs/USADEs have expedited reporting requirements. Any event that meets the definition of Unanticipated Adverse Device Effect (**Section 6.1**) must be reported to FDA, all investigators and reviewing IRBs within 10 working days after becoming aware of information that an unanticipated adverse device effect has occurred.

The site will notify the reviewing IRB within 10 working days after becoming of aware of the effect. The Sponsor will notify the all investigators, IRBs and the FDA within 10 working days after first receiving notification of the event. In addition, the Sponsor will comply with Medical Device Reporting / MDR regulations where applicable.

## **7 DEVICE SPECIFIC EVENT**

A device-specific event (DSE) is any malfunction or deficiency of the device.

Device deficiency is defined as inadequacy of a medical device with respect to its identity, quality, durability, reliability, safety or performance (ISO 14155:2011 3.15).

Malfunction is defined as failure of an investigational medical device to perform in accordance with its intended purpose when used in accordance with the Instructions For Use or Clinical Investigational Plan (ISO 14155:2011 3.27).

All device specific events must be reported to both the Sponsor and local authorities as required by governing law. If a device malfunction results in an adverse event for the subject, this adverse event will be considered a reportable adverse event and must be reported as an Adverse Event (AE).

## 8 STUDY COMMITTEES / CORE LABORATORY

To avoid and minimize bias, an independent Clinical Events Committee, Imaging Core Laboratory, and Data Safety Monitoring Board will be in place to assess event relationship, aneurysm occlusion, and vessel stenosis.

### 8.1 Clinical Events Committee (CEC)

A CEC will be in place for the study using a minimum of three (3) physicians knowledgeable in the appropriate disciplines and medical specialties pertinent to the disease state being evaluated in this clinical study. This committee will be responsible for the review and adjudication to the study endpoints of the following events reported by the site:

1. Events leading to sudden neurological worsening/deterioration  $\geq$  3 point NIHSS score
2. All Device related adverse events
3. All Procedure related adverse events

The CEC will independently adjudicate to specified endpoint event definitions, event relatedness, event severity, and event outcomes.

The CEC can request additional source documentation and any potential imaging obtained in support of the adverse event to assist with adjudication.

### 8.2 Imaging Core Laboratory

An imaging protocol will be provided to the site. The imaging core laboratory will be responsible for the qualitative image analysis to determine aneurysm occlusion, parent artery stenosis, and device migration.

#### 8.2.1 Baseline anatomy

Baseline imaging will be reviewed to assess baseline aneurysm and parent artery characteristics.

#### 8.2.2 Aneurysm Occlusion

Post-procedure angiograms will be reviewed to assess aneurysm occlusion according to the scale of Roy (Figure 2).

[figure not shown]

Figure 2. Scale of Roy for Judging IA Endosaccular Embolization Success

- **Complete** = Complete occlusion, no flow of contrast seen in the aneurysm sac
- **Residual Neck** = Partial occlusion, some flow or eddying flow in the aneurysm sac
- **Residual Aneurysm** = Incomplete occlusion, apparent flow in the aneurysm sac

Several published studies showed that the reliability of individual radiologist raters in judging complete vs. incomplete post-treatment occlusion was very high ( $\kappa=0.96$  and  $0.99$  for each rater). Moreover, inter-rater reliability of the complete vs. incomplete judgment was also reported to be very high ( $\kappa=0.87$ ; intra-class correlation coefficient (ICC)=0.76, 95% CI 0.69-0.82;  $P<0.0001$ ).

### 8.2.3 Parent Artery Stenosis

Post-procedure angiograms will be reviewed to assess stenosis in the parent artery across the entire Pipeline™ device. Vessel stenosis will be measured and judged according to the scale in **Table 6**.

**Table 6. Scoring System for Stenosis**

Category	Degree of Stenosis
0	0 – 25%
1	>25 – 50%
2	>50 – 75%
3	>75 – 100%

## 8.3 Data Safety Monitoring Board (DSMB)

The DSMB will be an independent group that will serve as a data monitoring committee to the Sponsor of this Study. The DSMB will be comprised of individuals who are independent of the investigational sites and of representatives from multiple disciplines including but not limited to neurology, biostatistics/epidemiology, neurosurgery and interventional neuroradiology.

In the safety monitoring role, this board shall provide recommendations to the Sponsor regarding stopping /continuing enrollment in the Study. In so doing, this board will propose interim analysis methodology with stopping rules related to Study safety. The DSMB will establish proposed monitoring criteria for the Study and will establish and document any required interim analysis time points for assessing safety. The group will also establish a mission statement and operating procedures.

The DSMB will also advise the Sponsor concerning the content of interim reports and the analyses that are required for data interpretation.

## 9 STATISTICAL METHODS AND DATA ANALYSIS

### 9.1 General Principles

Tabulations of summary statistics, graphical presentations, and statistical analyses will be performed using SAS software version 9.2 or higher. The statistical analyses will be based on data pooled across sites in aggregate, retaining site in the statistical models that allow for the inclusion of fixed effects. All subset summary tables and data listings will be sorted by subject and site. The pre-procedure observations will be used as the baseline value for calculating post-procedural changes from baseline.

Continuous demographic parameters, such as the age of the subject at the time of enrollment, will be summarized for the ITT population using descriptive statistics (N, mean, median, standard deviation, minimum and maximum value, and 95% 2-sided confidence limits). Categorical demographic parameters, such as gender, will be summarized as a proportion of the ITT population using Clopper-Pearson 95% 2-sided confidence limits. Clinical and high risk factors will also be summarized as a proportion of the ITT population with Clopper-Pearson 95% 2-sided confidence limits.

Data obtained during the neurological examination using the Modified Rankin will be summarized at each time point using descriptive statistics.

Adverse events will be coded according to the MedDRA system dictionary. The percentage of subjects experiencing adverse events will be summarized by body system and preferred term. Subject counts will be tabulated for all adverse events for the ITT population. Adverse events will also be tabulated for events that occurred within the first 30 days of the procedure. Tabulated subject counts will be presented as a proportion of the ITT population with 95% binomial confidence intervals.

Summarizations predicated on continuous variables will be based on a generalized linear model, predicated on maximum likelihood, specifying the dependent variable as a variable with a continuous distribution. The single factor included in the model will be site. The baseline scores for specific parameters may be added to the analysis to increase the precision of the model. Probability values <0.05 will be considered significant.

Summarizations predicated on proportions will be based on a generalized linear model, predicated on maximum likelihood, specifying the dependent variable as a dichotomous variable with a binomial distribution. The single factor included in the model will be site.

The analyses predicated on ordinal categorical parameters will be based on a generalized linear model, predicated on maximum likelihood, specifying the dependent variable as a categorical variable with a multinomial distribution. The single factor included in the model will be site.

Specific algorithms for imputing missing or partially missing dates will be discussed in the Statistical Analysis Plan. Derived data will be identified in the individual subject data listings. Imputed data for dates will not be incorporated into the case report form datasets. Imputed data for dates will be used in the preparation of the derived datasets.

Small sites (i.e., sites that have less than 4 subjects) will be identified and the following method will be used for combining the data. Data from all small sites (<4 subjects) will be combined to form a single site in order to obviate non-estimable situations in the evaluation of site and site interaction effects. Once combined, the pooled site will remain as such for all analyses for which a site effect is determined. If the pooled smaller sites represent a single site that has more than twice as many subjects as the largest single site, however less than 3 times as many subjects, the small sites will be ranked by size and divided into 2 pooled assignments using an alternating sequence (ABABAB). If the pooled smaller sites represent a site that has more than three times as many subjects as the largest single site, however less than 4 times as many subjects, the small sites will be ranked by size and divided into 3 pooled assignments using an alternating sequence (ABCABCABC).

To understand the potential effect of a site effect, *site* will be included as a covariate in a logistic regression model, designating the occurrence of major stroke in the territory supplied by the treated artery or neurological death at 1 year as the dependent variable and calculating the Breslow-Day test of homogeneity of the odds ratios. A probability value less than 0.05 will be considered evidence of a significant difference among the sites. Under this scenario, *site* would be retained in the model for calculating the adjusted confidence intervals. The intra-site event rate will also be displayed graphically using exact 95% binomial confidence limits.

To understand the potential effect of a Site effect on the primary performance endpoint, *Site* will be included as a covariate in a logistic regression model, designating the 1 year post-procedure aneurysm occlusion as the dependent variable and calculating the Breslow-Day test of homogeneity of the odds ratios. A probability value less than 0.05 will be considered evidence of a significant difference among the sites. Under this scenario, *Site* would be retained in the model for calculating the adjusted confidence intervals. The intra-site event rate will also be displayed graphically using exact 95% binomial confidence limits.

In the absence of data to suggest otherwise, a subject who does not attend the 1 year post-treatment visit in the allotted time window will not be considered a primary safety endpoint failure unless it is known that the subject experienced stroke or death.

All recorded data will be presented in the individual data listings.

## 9.2 Sample Size Calculation

Estimates were prepared separately for the primary safety and performance endpoints and based on generating a 1-sided 97.5% Clopper-Pearson exact binomial confidence interval. The upper bound of the confidence interval for safety and the lower bound for performance will be examined relative to the respective *a priori* thresholds. For the primary safety endpoint, the null and alternative hypotheses are as follows:

Ho: Incidence at 1 year post-procedure of major stroke in the territory supplied by the treated artery or neurological death  $\geq 0.15$

Ha: Incidence at 1 year post-procedure of major stroke in the territory supplied by the treated artery or neurological death  $< 0.15$

Reasonable estimates of the observed rate were considered to range between 5% and 9%; the sample size estimates under these scenarios are presented in **Table 7** below:

**Table 7. Observed Incidence at 1 Year Post-Procedure of Major Stroke in the territory supplied by the treated artery or Neurological Death**

Observed Incidence at 1 Year	Minimum Sample Size
5%	52
6%	63
7%	80
8%	104
9%	141

For the primary effectiveness endpoint, the null and alternative hypotheses are as follows:

Ho: Incidence at 1 year post-procedure of aneurysm occlusion without significant parent artery stenosis  $\leq 0.50$

Ha: Incidence at 1 year post-procedure of aneurysm occlusion without significant parent artery stenosis  $> 0.50$

Reasonable estimates of the observed rate were estimates at 61% to 65%; the sample size estimates under these scenarios are presented in **Table 8** below:

**Table 8. Observed Incidence at 1 Year Post-Procedure of Aneurysm Occlusion Without Significant Parent Artery Stenosis**

Observed Incidence at 1 Year	Minimum Sample Size
61%	100
62%	83
63%	71
64%	61
65%	53

The maximum number of subjects to be enrolled in this clinical investigation will be 141 subjects, based on an incidence at 1 year of major stroke in the territory supplied by the treated artery or neurological death of 9%. Based on the expected incidence of the primary endpoints, a minimum of 80 subjects will be enrolled.

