## PROTOCOL SYNOPSIS

Sponsor: Covidien - Neurovascular [name] [name] Telephone:	Protocol Number: NV-PED-07
	Product: Pipeline™ Embolization Device 
	Regulatory Class: III
	Development Phase: IV

Currently, treatment with the Pipeline™ device is indicated for IAs in the ICA from the petrous to the superior hypophyseal segments and the present study aims to include IAs in the ICA up to the terminus. Data from 277 patients with IAs ≤ 12 mm located in the ICA up to the terminus were collected in the IntrePED retrospective study, which demonstrate neurological morbidity and mortality rates of 2.9% and 1.1%, respectively. These rates demonstrate that the Pipeline™ device can serve as a potentially safe treatment option for IAs of the ICA (up to the terminus). The treatment of IAs in the posterior circulation is typically associated with a higher rate of complications. However when limited to only the vertebral and posterior inferior cerebellar arteries, published literature indicates that the morbidity and mortality rates are similar to the rates reported for stent-assisted coil treatment of small-wide-necked IAs. Studies evaluating the treatment of aneurysms located in the VA or PICA demonstrate morbidity rates ranging 0%-13% and mortality rates ranging 0%-7%. These rates are comparable to the stent-assisted coiling morbidity rates of 3.9%-9.2% and mortality rates of 0%-6.8%. Within this current study, the safety and effectiveness of the Pipeline™ device for the treatment of unruptured wide-necked IAs measuring ≤ 12 mm in the vertebral artery segment up to and including the PICA will be investigated.

Number of Subjects: Up to 200 subjects enrolled to ensure 141 treated subjects	Number of Study Centers: Up to 28 study centers
--	---

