### 4.1 Number of Sites and Subjects

Up to 200 subjects will be enrolled at up to 28 sites worldwide over a period of approximately 18 months to ensure the study has an adequate number of treated subjects; up to 141 (see **Section 9.2**). The enrollment number takes into account an approximate 30% screen failure rate observed in the initial roll-out of the PREMIER study. Each participating investigational site will be allowed to enroll a maximum of 25 subjects who meet all study eligibility criteria (see **Section 4.3**) and are treated with the Pipeline™ device.

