### 4.2 Expected Duration of the Study and Subject Participation

Up to 141 subjects who meet the eligibility criteria (see **Section 4.3**) and are treated with the Pipeline™ device will actively participate for up to 3 years. Study participation includes consent, initial screening and baseline, treatment using the Pipeline™ device, discharge exam and follow-up visits at 30 days, 180 days, 1 year, 2 years, and 3 years.

The total study duration is expected to be approximately 54 months.

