***Subjects are considered enrolled in the study once the subject signs the study Informed Consent Form.***

It is the responsibility of the Investigator to give each subject (or subject's legally authorized representative) prior to inclusion in the study, full and adequate verbal and written information regarding the objective of this study and the confidentiality of the data collected.

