Modified Rankin Scale (mRS)	Scale for measuring general neurologic function. 0 No symptoms at all 1 No significant disability despite symptoms; able to carry out all usual duties and activities 2 Slight disability; unable to carry out all previous activities, but able to look after own affairs without assistance 3 Moderate disability; requiring some help, but able to walk without assistance 4 Moderately severe disability; unable to walk without assistance and unable to attend to own bodily needs without assistance 5 Severe disability; bedridden, incontinent and requiring constant nursing care and attention 6 Dead
Neck	Width of the opening of the aneurysm where it meets the parent vessel.
Neurological Adverse Event	An adverse event with an underlying neurological cause.
Neurological Death	Subject death due to neurologic reasons.
Per protocol (PP) population	All enrolled subjects, had the Pipeline™ device successfully implanted, and completed the study without any major protocol deviations.
Point of Enrollment	Point at which the subject signs the study Informed Consent Document.
Procedure-related Adverse Event	Event has a strong temporal relationship to the procedure (Day 0).
Procedure time	Start: Time of first Pipeline™ device introduction (i.e., once the Pipeline™ device is advanced into the microcatheter inside the blood stream of the subject.) End: Time of last Pipeline™ device delivery system removal
Retreatment	Any subsequent intervention (post procedure) performed to treat the target IA.
Screen Failure	Screened patient not enrolled in the study.
Serious Adverse Event (SAE)	An adverse event that: a) Led to death, b) Led to serious deterioration in the health of the subject, that either resulted in a. A life-threatening illness or injury, or b. A permanent impairment of a body structure or a body function, or c. In-subject or prolonged hospitalization, or d. Medical or surgical intervention to prevent life-threatening illness or injury or permanent impairment to a body structure or a body function, c) Led to fetal distress, fetal death or a congenital abnormality or birth defect (ISO 14155:2011 3.37)
Serious Adverse Device Effect (SADE)	An adverse device effect that has resulted in any of the consequences characteristic of a serious adverse event. (ISO 14155:2011 3.36)
Small Intracranial Aneurysm	< 7 mm

TERM	DEFINITION

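### Section 9.2 caps enrolled (consented) subjects at 141, while the rest of the protocol makes 141 the treated number with up to 200 enrolled; 141 also rests on an observed-rate criterion with no stated power

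*Combined protocol and SAP*

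**What the plan says.** **Size in Section 9.2.** After Table 8, the plan sets the upper limit: "The maximum number of subjects to be enrolled in this clinical investigation will be 141 subjects, based on an incidence at 1 year", the incidence being 9% for major stroke in the treated territory or neurological death. The lower limit follows: "Based on the expected incidence of the primary endpoints, a minimum of 80 subjects will be enrolled".

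**Meaning of enrolled.** Section 5.2: "Subjects are considered enrolled in the study once the subject signs the study Informed Consent Form". Section 21, Point of Enrollment: "Point at which the subject signs the study Informed Consent Document".

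**Size elsewhere.**
- Synopsis, Number of Subjects: "Up to 200 subjects enrolled to ensure 141 treated subjects".
- Section 4.1 enrols up to 200 "to ensure the study has an adequate number of treated subjects; up to 141", points to Section 9.2 for that number, and explains the 200 by a screen-failure rate of about 30%.
- Section 4.2: "Up to 141 subjects who meet the eligibility criteria" and are treated take part for up to 3 years.
- Section 9.3 builds the analysis population from 141 treated subjects.

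**Basis for 141.** Section 9.2 introduces Table 7 with: "Reasonable estimates of the observed rate were considered to range between 5% and 9%; the sample size estimates under these scenarios". The table gives 52, 63, 80, 104 and 141 for 5% to 9%. Success means a one-sided 97.5% Clopper-Pearson upper bound below 15%. Table 8 covers effectiveness, with planning rates of 61% to 65% and a lower bound to exceed 50%. Neither table, nor any other section, gives design power at a true rate.

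**The concern.** Two things in the paragraph that fixes the trial's size do not fit.

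First, the unit. A cap on consented subjects and a target for treated subjects are different quantities when the protocol itself expects about 30% loss between them. Section 4.1 sends the reader to 9.2 for the treated number, and 9.2 gives that number as an enrolment maximum. Anyone applying the 9.2 maximum under the protocol's own definition would stop consenting well short of 141 treated.

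Second, the justification. Table 7 is headed as an observed incidence, but the closing sentence drops that qualifier and bases 141 on an incidence of 9%. Coming after formal hypotheses and under the title of a sample size calculation, this can be read as saying that 141 is enough if the true rate is 9%. What 141 delivers at a true 9%, or at any other true rate, is not stated.

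**Working it through.** **Inputs.** One-sided 97.5% exact Clopper-Pearson bounds; thresholds 15% (safety) and 50% (effectiveness); planning rates 5-9% and 61-65% (all Section 9.2); about 30% screen failure (Section 4.1); up to 200 enrolled (synopsis, 4.1).

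**1. Reproduce Table 7.** The upper bound for x events in n is U(x, n), the 0.975 quantile of Beta(x+1, n-x). Put x = p × n without rounding and take the smallest n with U < 0.15.

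| Observed rate | n | x = p × n | U |
|---|---|---|---|
| 5% | 52 | 2.60 | 14.87% |
| 6% | 63 | 3.78 | 15.00% (just below) |
| 7% | 80 | 5.60 | 14.97% |
| 8% | 104 | 8.32 | 14.98% |
| 9% | 141 | 12.69 | 14.99% |

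All five sizes match the plan. The calculation has no power term, and in every row the count is not a whole number.

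**2. Whole counts at n = 141.**
- 12 events: 12/141 = 8.5%, U = 14.39%, passes.
- 13 events: 13/141 = 9.2%, U = 15.25%, fails.

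Safety success with 141 subjects therefore means at most 12 events.

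**3. Safety power with 141 treated**, P(X ≤ 12), X ~ Binomial(141, p):

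| True rate | 5% | 6% | 7% | 8% | 9% |
|---|---|---|---|---|---|
| Power | 97.5% | 91.8% | 81.1% | 66.1% | 49.4% |

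**4. Effectiveness power with 141 treated.** The lower bound L(x, n) is the 0.025 quantile of Beta(x, n-x+1). L(83, 141) = 50.27% passes and L(82, 141) = 49.56% fails, so at least 83 successes are needed. P(X ≥ 83):

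| True rate | 61% | 62% | 63% | 64% | 65% |
|---|---|---|---|---|---|
| Power | 72.9% | 80.4% | 86.5% | 91.2% | 94.6% |

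**5. Which unit fits the rest of the protocol.** 141 / 0.70 = 201.4, in line with up to 200 enrolled; conversely 141/200 = 70.5%, an implied loss of 29.5%. So 141 has to be the treated number. The gap between the two enrolment limits is 200 - 141 = 59.

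**6. The 9.2 maximum taken literally.** 141 × 0.70 = 98.7, so about 98 to 99 treated. At both sizes at most 7 events pass (U = 14.16% and 14.03%) and 8 fail.

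| Treated | Power at true 7% | Power at true 9% |
|---|---|---|
| 98 | 62.0% | 33.5% |
| 99 | 61.0% | 32.4% |
| 141 | 81.1% | 49.4% |

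This step assumes that the 30% acts between consent and treatment, which is how Section 4.1 uses it to get from 200 to 141.

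**The case against.** The intended unit can be recovered. Four other places give 141 as treated, and the reference to 9.2 in Section 4.1 is attached to the treated figure. A site or sponsor reading the whole protocol would probably not stop at 141 consents. That stands as a reason not to overstate the practical risk. It does not remove the conflict, which is between current passages and lies in the section that the others cite.

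On power, the plan claims none, and 141 is correctly computed for the criterion used. The 9% row is the top of the planning range and sets a maximum; the plan links its expected incidence to the 80, which is the 7% row, and at 7% the power with 141 is 81.1%. Section 9.6 adds a conditional-power review that may adjust the size. All of this is fair. But that review gives no design power either: its only power figure is the 50% conditional-power condition for leaving alpha unadjusted. It supplements a power statement and does not replace one.

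A reader might go further and infer that 141 is miscalculated or that the trial is too small. The documents do not support either. Table 7 reproduces exactly. At the 5.6% one-year rate reported in Section 1.2.3 for the earlier single-arm trial of this device (larger aneurysms), power with 141 is 94.6%. At the pooled retrospective rate for small and medium aneurysms in Table 3, (9 + 1)/(221 + 19) = 10/240 = 4.2% on a different endpoint, it is 99.4%. Nor can one infer a planned analysis at 80: Section 9.3 plans 141 treated, and Section 9.2 attaches no stopping rule to the minimum.

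**Conclusion.** The point holds as an internal inconsistency in a stated sample size, together with an incompletely stated justification. It should be corrected.

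- **Unit.** The 141 in Section 9.2 is labelled enrolled where every other section requires treated, and the enrolment limit of up to 200 is missing there. The minimum of 80 carries the same label. That it means treated is only an inference from its match to the 7% row of Table 7; no section says so.
- **Basis.** 141 is right for an observed-rate criterion with an unrounded count. It is not a guarantee at 9%: no whole count gives 9% of 141, the nearest (13) fails, and a true 9% gives roughly an even chance of success. Safety power is above 80% at true rates up to 7% and below it at 8% and 9%. Effectiveness power is below 80% only at 61% within the planning range.

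The power figures assume independent binomial outcomes and exactly 141 subjects in the primary analysis; the cut-offs of 12 and 83 belong to that size. The fault lies in the wording and the stated basis. The number of patients looks adequate on the protocol's own earlier data.

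**What to change.** In Section 9.2:

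1. Say *treated* for the 141, and state the cap of up to 200 enrolled, as in the synopsis and Section 4.1.
2. Have the sponsor confirm whether the minimum of 80 means treated subjects, and label it accordingly.
3. Replace the basis with wording such as: *141 was obtained as the size at which an observed incidence of 9%, calculated with an unrounded count, has an upper 1-sided 97.5% Clopper-Pearson bound below 15%. With whole counts at n = 141 the criterion is met by at most 12 events (8.5%). It is not a power calculation.*
4. Add the two exact power tables from steps 3 and 4, for true safety rates of 5-9% and true effectiveness rates of 61-65%. Mark the cut-offs (at most 12 events, at least 83 successes) as applying to n = 141.

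In Section 9.6, change the 50 subjects *enrolled* to *treated*, to match the Statistical Analysis part of the synopsis.

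The cost is wording and a short table. No patients, visits, thresholds or tests change. The only downside is that the plan will show less favourable power at safety rates of 8-9% and at 61% effectiveness.
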